#### 6.3.3 Treatments and concomitant interventions allowed and prohibited during the study

The use of concomitant medications by any route of administration during the intervention period will not be allowed. Except those specified for the study procedures. The objective of this restriction is to avoid pharmacological interactions that could alter the results of the evaluated variables.

#### 6.3.4 Treatment management

The interventions will be provided by Sophia Laboratories A.S. of V.C., for each research center. They will be labeled, reconciled and weighed previously. The handling of the treatment will be under the responsibility of the investigator or a designated member of his team.

#### 6.3.4.1 Delivery and reception

The delivery will be made in closed cardboard boxes by means of a courier service or directly by the sponsor's staff to the address of the research center according to the study plan.

The reception will be exclusively carried out by the research center team, including the researcher. You must check the good condition of the primary packaging (box). In the event that it shows alterations or defects in its integrity that from its judgment could have damaged the content, it should report it to the sponsor. If the package does not show significant defects, it will proceed to open it.

Inside you must locate the acknowledgment document and the logger (data logger) of temperature and humidity. You should check that the registered temperature and humidity comply with the specifications for transport and shelter (see section 6.3.4.2 Storage). Verify the content (interventions) with what is reported in the document. In case the document corresponds to the content, it will sign the receipt and send it to the sponsor. Otherwise, notify the sponsor.

In the study center, the personnel assigned by the PI will deliver the corresponding treatment to the subjects admitted, sufficient for the period to be covered. Delivery will be made in stages, medication will be delivered at the baseline visit and visit 1. The center must register the medicine delivered

#### 6.3.4.2 Storage

The medication must be stored in a secure area with restricted access.

The storage temperature should be at room temperature to no more than 25° Celsius.

The research center has the obligation to record, in the format designated by the sponsor, the temperature and humidity registered in the data logger. This record should include the current temperature and humidity, as well as the minimum and maximum of each of these. It must be done at least once a day, on business days.

Said data will be compared by the clinical monitor according to the registration in the data logger.

#### 6.3.4.3 Return

The research subjects will return to the staff indicated by the IP in the center their treatments in visits 1 and final. The refund will be made by the research center when the sponsor indicates it. Prior to the return the research center must make a count of the assigned medication and the remaining medication, with the aim of creating an inventory which serves for the final filling of the return form of the medication.

# 6.4 Outcome variables

# 6.4.1 Security variables

# 6.4.1.1 Primary outcome variables

- Globet cell density
- Epithelial defects in cornea and conjunctiva.
- Presence of adverse events.

#### 6.4.1.2 Primary outcome variables of tolerability

- Burning
- Foreign body sensation
- Itching
- Eye comfort index

#### 6.4.1.3 Secondary outcome variables

- Intraocular pressure
- Visual ability
- Laboratory tests: BHc, QS and PFH.
- Ophthalmological signs: conjunctival hyperemia, chemosis.
- Rupture time of the tear film
- Life signs: FC, FR, TAS.
- Subsequent segment
- Quality questionnaire

#### 6.4.2 Efficacy variables

# 6.4.2.1 Primary outcome variables

It does not apply because it is a phase I study

6.4.2.2 Secondary outcome variables

It does not apply because it is a phase I study

CONFIDENTIAL

6.4.3 Methods and scales to be used for the measurement of the variables

Variable	Unit	Symbolo	Type	Method of measurement	Normal value
Age	years		Continuous	Calculation from the day of birth	NA
Gender	Female/ Male	F/M	Nominal	Direct questioning	NA
Adverse events	Number of cases	n	Discreet	Conteo	NA
Intraocular presure	Milimeters of mercury	mmHg	Continuous	Goldman's applanation tonometry	11 - 21
Visual ability	Fraction	Snellen	Nominal	Chart	
Tear rupture time	Seconds	S	Continuous	Direct counting	> 10
Eye confort index	Points		Discreet	Questioning	
Adverse events	Present / Absent		Nominal	Comprehensive assessment	Absent
Goblet cell density	Cells per square milimeter	Cel/mm 	Continuous	Citology per impression	> 500 cell/mm
ital signs					
Heart rate	Beats per minute	lpm	Discreet	Auscultation	60 – 100
Breathing frequency	Breaths per minute	rpm	Discreet	Auscultation	12 – 24
Systemic blood pressure	Milimeters of mercury	mmHg	Continuous	Non-invasive auscultatory measurement	< 120 / 80
nterior segment					
Epithelial defects	Degrees		Discreet	Direct observation with green lysine and fluorescein stains	Oxford Scale
)phthalmologic signs an	d symptoms				
Conjunctival hiperemia	Normal / Very Light / Mild / Moderate / Severe		Ordinal	Direct observation.  Classification of Efron	Normal
Chemosis	Present / Away		Nominal	Direct observation	Absent
Burning	Severity: Absent, very mild, mild,		Nominal	Direct questioning	Absent

Version: 1.0

# **CONFIDENTIAL**

Variable	Unit	Symbolo	Туре	Method of measurement	Normal value
	moderate and severe				
	Frequency: At all times, almost at all times, 50% of the time, almost in no time, at any time.				
	Severity: Absent, very mild, mild, moderate and severe				
Foreign body sensation	Frequency: At all times, almost at all times, 50% of the time, almost in no time, at any time		Nominal	Direct questioning	Absent
Pruritus	Severity: Absent, very mild, mild, moderate and severe Frequency: At all times, almost at all times, 50% of the time, almost in no time, at any time	-	Nominal	Direct questioning	Absent
Post-application sympto					
Burning	Present / Away		Nominal	Journal of the subject	Absent
Sensación de cuerpo extraño	Present / Away		Nominal	Journal of the subject	Absent
Prurito	Present / Away		Nominal	Journal of the subject	Absent
Ojo rojo (síntoma)	Present / Away		Nominal	Journal of the subject	Absent
posterior segment					
Macula	Normal / Abnormal		Nominal	Direct observation	Normal
Optical disk integrity	Normal / Abnormal		Nominal	Direct observation	Normal
Blood count					
Erythrocytes		M/uL	Continuous		

# **CONFIDENTIAL**

Variable	Unit	Symbolo	Туре	Method of measurement	Normal value
Hemoglobin	Grams over deciliter	g/dL	Continuous		
Hematocrit	Porcentage	%	Continuous		
VGM	Femto liters	fL	Continuous		
НСМ	picograms	pg	Continuous		
CMHbG	Grams over deciliter	g/dL	Continuous		
Leukocytes	Thousands per liter units	Mil/uL	Continuous		
Platelets	Thousands per liter units	Mil/uL	Continuous		
Myelocytos	Porcentage	%	Discreet		
Metamyelocytos	Porcentage	%	Discreet		
Bands	Porcentage	%	Discreet		
Segmented	Porcentage	%	Discreet		
Lymphocytes	Porcentage	%	Discreet		
Monocytes	Porcentage	%	Discreet		
Eosinophils	Porcentage	%	Discreet		
Basophils	Porcentage	%	Discretet		
Blastos	Porcentage	%	Discreet		
Blood chemistry					
Glucose	Milligrams on deciliter	mg/dL	Continuous		
Urea	Milligrams on deciliter	mg/dL	Continuous		
Creatinine	Milligrams on deciliter	mg/dL	Continuous		
Liver function tests					
Alanine transferase	Units on liter	U/L	Continuous		
Aspartate transferase	Units on liter	U/L	Continuous		
Total Bilirrubin	Milligrams on	mg/dL	Continuous		
	deciliter				

Version: 1.0

#### CONFIDENTIAL

Variable	Unit	Symbolo	Туре	Method of measurement	Normal value
Indirect Bilirrubin	Milligrams on deciliter	mg/dL	Continuous		

Table 4. Scales to be used

The following describes the methods and scales that will be used to measure the variables, which are in strict alphabetical order:

#### 6.4.3.1 Visual ability

Visual acuity (VA) is a test of visual function. Spatial visual acuity is the ability to distinguish separate elements of an object and identify them as a whole. It is quantified as the minimum separation angle (located at the nodal point of the eye) between two objects that allows perceiving them as separate objects.

Snellen's notation is described as the distance at which the test is performed, divided by the distance at which the letter is vertically equivalent to 5 arc minutes. Thus, at 6 meters a letter 6/6 (20/20) equals 5 minutes of arc, a letter 6/12 (20/40) equals 10 minutes, and a letter 6/60 (20/200) equals 50 minutes The Snellen fraction can also be expressed as a decimal (ie 20/20 = 1 and 20/40 = 0.5). [38]

The VA will be evaluated basally, without refractive correction with the Snellen chart. Which will be located in a place with adequate lighting, natural or artificial and at a distance of 3m from the subject to be evaluated. The visual acuity of each eye will be taken, starting with a right eye (DO) asking the subject to keep both eyes open and using an occluder to cover the left eye (OS); the subject will read aloud the lines that the evaluator points out, the line of smaller letters that he reaches to see will be annotated by the fractional evaluator as the DO of the DO in the clinical record. Proceed to the OS with the same method.

Subsequently the best refractive correction of the subject will be made and the examination will be repeated using the obtained refraction. This result will be reported as CV, it will be written in fraction in the clinical file and in the CRF, in addition in the CRF it will be written in decimal. By definition, the CV can not be inferior to the AV.

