## 6.5 Timeline and study diagram

Procedures	scrutiny	Basal visit	Visit 1	Final visit	Call Security
Procedures		Day 0	Day 3 ± 1	Day 11 ± 1	Day 13 ± 1
CI signature	Х				
clinic history	Χ				
Ophthalmological clinical history	Х				
Laboratory sample taking	Χ			Χ	
Laboratory tests review		Х			Х
Pregnancy test	Χ			Χ	
Eligibility criteria	Х	Xa			
Assignment		Χ			
Delivery of intervention		Х	Х		
Return of intervention			Χ	Χ	
Adherence evaluation			Х	Х	
Adverse events			Х	Χ	Χ
Intraocular pressure	Х	X 	Х	Х	
Visual ability	Χ	X 	Χ	Χ	
TRL	Х	X 	Х	Х	
Epithelial defects (TF and TVL)	Χ	X 	Х	Χ	
Eye signs and symptoms	Х	X 	Х	Х	
Posterior Segment	Χ	X 		Χ	
Vital signs	Х	X 	Х	Х	
Ocular Comfort Index		Х		Х	
Goblet cell density (cytology by impression)		Х		Х	
Daily delivery of the subject		Χ	Х		
Return / Evaluation of the subject's Journal			Х	Х	
Delivery Quality Questionnaire		Χ			
Return and Evaluation of the quality questionnaire				Х	
Continuity evaluation of the subject		Х	X	X	

a The eligibility criteria will be completed with the revision of the laboratory exams. 1 These measurements may be taken from the result of the screening visit, if it does not exceed the previous 7 days. It is the prerogative of the PI to decide whether to repeat the measurements at the baseline visit.

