#### 8.3 Statistical methodology

#### 8.3.1 Analysis of primary and secondary outcome variables

The statistical analysis will be carried out by personnel of Sophia Laboratories. The statistical program SPSS version 19 (IBM Corporation, Armonk, NY, USA) will be used.

The designated personnel will be blinded to the intervention groups. The coding will be done using consecutive numbers for each intervention group.

The data will be collected and sorted in an excel sheet. Later they will be exported to the platform of the SPSS program. The variables will be categorized according to their nature.

The result of the continuous quantitative variables will be presented in measures of central tendency: mean, standard deviation and ranges. See Table 4. Scales to be used

The normal distribution of the results will be obtained by the Kolmogorov-Smirnov test.

The statistical analysis of the continuous **quantitative variables** to find significant differences (p) will be the following:

- Intra-group analysis: Wilcoxon rank test.
- Inter-group analysis: Mann-Whitney U test.

The level of difference to consider significance will be an alpha of 0.05 or less.

The result of nominal and ordinal qualitative variables will be presented in frequencies, proportions and percentages.

The statistical analysis to identify significant differences of the **qualitative variables** will be done creating 2x2 contingency tables and it will be carried out in the following way:

- Intra-group difference: McNemar or Pearson test.
- Difference between groups: test χ2 (Chi-square) of Pearson.

The level of difference to consider significance will be an alpha of 0.05 or less.

For the reporting of adverse events all eyes of those participants who were randomly assigned to an intervention group after the baseline visit will be considered. The results will be expressed in number of cases (eyes).

The final report of the results will be shown in tables or graphs, as appropriate.

It will be considered that the investigational drug is safe and tolerable when there are no clinical and statistical differences in all the variables of primary outcome, with respect to its comparator.

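### Visual ability, a secondary safety outcome, is typed nominal and sent to a 2x2 chi-square with no cut-point, and the between-group comparison is not specified as change from baseline

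*Combined protocol and SAP*

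**What the plan says.** - **Type.** The Table 4 row in section 6.4.3 reads "Visual ability Fraction Snellen Nominal Chart". Its normal-value cell is empty.
- **Recording.** Section 6.4.3.1 explains that "The Snellen fraction can also be expressed as a decimal (ie 20/20 = 1 and 20/40 = 0.5"), and for best-corrected visual capacity adds that "in addition in the CRF it will be written in decimal".
- **Timing.** Section 6.5 schedules the measurement at screening, baseline, visit 1 and the final visit, but not at the day 13 call. For baseline, "These measurements may be taken from the result of the screening visit, if it does not exceed the previous 7 days".
- **Analysis.** Section 8.3.1 refers to Table 4 for the nature of the variables. For qualitative variables, nominal and ordinal, the analysis "will be done creating 2x2 contingency tables and it will be carried out in the following way". Between arms this is "Difference between groups: test χ2 (Chi-square) of Pearson"; within arms it is McNemar or Pearson. Continuous variables get Mann-Whitney between arms and Wilcoxon within arms.
- **Role.** Section 5.5.2 makes change in visual ability a specific safety objective. Section 6.4.1.3 lists visual ability as a secondary outcome. The criterion in 8.3.1 for calling the product safe and tolerable names the primary outcome variables only.

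**The concern.** Snellen acuity is ordered, the CRF holds it as a number, and each subject has a value from before treatment. The declared type places it with variables that have no order, and the prescribed 2x2 table needs a split that the plan does not define. The analyst would have to choose that split later.

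The between-group test is also not tied to change, although change is the objective. In healthy volunteers who enter at 20/30 or better, the event of interest is a fall of a line or two from the subject's own starting value. A table of final values mixes that fall with differences in acuity that were present at entry. A real difference could then be reported as none on a secondary safety objective.

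**Working it through.** **1. Inputs from the documents.** Twelve subjects per arm, one eye each (6.6.1); alpha 0.05 (8.3.1); entry at 20/30 or better (6.2.1). The plan gives no power figure for visual ability. Its only computed figure is the total sample size, 19/(1 - 0.20) = 23.75, rounded up to 24. That rests on tolerance and serves here only to fix 12 per arm.

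**2. What the prescribed table can detect, whatever the cut.** For a 2x2 table with cells a, b, c, d, Pearson chi-square = N(ad - bc)² / (product of the four margins).

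- 0/12 v 3/12: 24 x 36² / (12 x 12 x 3 x 21) = 3.43, p = 0.064.
- 0/12 v 4/12: 24 x 48² / (12 x 12 x 4 x 20) = 4.80, p = 0.028. The smallest expected count is 2, and Fisher's exact test gives p = 0.093.

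So if no subject crosses in one arm, at least four of twelve must cross the undefined cut in the other. With a cut at the 20/30 entry limit, a fall from 20/15 to 20/30 would not count at all.

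**3. Power under assumed losses.** None of these rates is in the documents. Baseline at 20/20, 20/25 and 20/30 is 60/25/15% or, alternatively, 80/15/5%. In one arm 35% lose one line and 15% lose two; in the other 10% lose one line. There is no measurement noise. Expected proportions:

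- Final value 20/20, first baseline: 0.60 x 0.50 = 30% v 0.60 x 0.90 = 54%, a gap of 24 points.
- Final value 20/20, second baseline: 0.80 x 0.50 = 40% v 0.80 x 0.90 = 72%, a gap of 32 points.
- Any line lost, either baseline: 50% v 10%, a gap of 40 points.

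Simulated power, 4,000 trials per scenario, chi-square without continuity correction:

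| Comparison | Baseline 60/25/15 | Baseline 80/15/5 |
|---|---|---|
| Chi-square, final 20/20 v worse | about 24% | about 40-41% |
| Mann-Whitney, final value | about 25% | about 37% |
| Chi-square, at least one line lost | about 60% | about 60% |
| Mann-Whitney, change | about 60% | about 60% |

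The two final-value rows are alike and the two change rows are alike. The endpoint makes the difference; the choice of test makes almost none.

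**4. Sensitivity to noise.** A second set of assumptions adds random shifts of one line, 10% in each direction, baselines that include 20/15, and a one-line loss in 50% of one arm (3,000 trials per scenario).

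| Comparison | Power |
|---|---|
| Chi-square, cut at 20/30 | 1-5% |
| Chi-square, cut at 20/20 | 13-27% |
| Mann-Whitney, final value | 14-21% |
| Mann-Whitney, change | 54-55% |

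With no true difference, the change test rejected in at most about 2.5% of trials under either set of assumptions, so its advantage is not bought with false positives.

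**The case against.** The strongest reply is that the nominal label does little harm in itself. A 2x2 chi-square on whether a subject lost at least one line performs as well as Mann-Whitney on change, and Mann-Whitney on final values does no better than chi-square. The plan does not say that its table uses final values; given the objective in 5.5.2, a table of worsened versus not worsened would fit the text equally well. The 20/20 cut and the loss rates are assumptions, and losses in half of an arm of healthy volunteers are a large effect. All of this stands. It moves the weight of the point from the label to the missing definition of the comparison.

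Three stronger readings are tempting and are not supported:

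- *That the plan discards the baseline.* McNemar, one of the two within-group options, is a paired test and can use dichotomised baseline values. The gap is in the between-group comparison. It is not special to nominal variables either, because the Mann-Whitney test for continuous variables is not specified as change.
- *That visual ability is a key safety variable, so that a missed loss counts toward declaring safety.* It is secondary, and the criterion in 8.3.1 uses primary outcomes only.
- *That a fresh decimal value exists at every contact.* It is taken at clinic visits only, and the baseline may be the screening value if that is no more than 7 days old.

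**Conclusion.** The point holds as a gap in specification for a secondary safety outcome. The type in Table 4 does not match the ordered decimal value that the CRF collects, the 2x2 table has no cut-point, and the between-group comparison is not tied to the baseline although the objective is change.

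Under the assumed losses without measurement noise and 12 per arm, comparing change gives about 60% power, against about 24-41% for a chi-square on final 20/20 versus worse and 24-38% for Mann-Whitney on final values. These figures show direction and rough size only, since the documents supply no loss rates. Even the better analysis falls short of 80% for an effect this large, so the analysis remains exploratory. The primary outcomes, the safe-and-tolerable criterion and the sample size are unaffected. This is a low-priority improvement.

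**What to change.** 1. In Table 4, retype visual ability as ordinal or quantitative.
2. In 8.3.1, state that change from baseline in decimal or logMAR visual capacity of the treated right eye is compared by Mann-Whitney between arms and Wilcoxon within arms. This sentence is needed as well as the retyping: an ordinal variable would otherwise still go to the 2x2 tables, and a quantitative one would still lack any mention of change.
3. If a 2x2 table is kept, define it in advance on lines lost from baseline, for example at least one line lost or not, rather than on final values.
4. State which value is the baseline when the screening measurement is carried forward.

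The cost is wording in the analysis plan. The values are already scheduled and recorded, so no visit, measurement or subject is added.

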## 6.4.3.2 Goblet cell density (Cytology per impression)

The density of goblet cells in the conjunctiva can be a reflection of the severity of alteration in the ocular surface. [39] It has been determined that the normal density is greater than 500 cel / mm2. [40] Impression cytology refers to the application of a cellulose acetate filter to the ocular surface to remove the superficial layers of the epithelium; these removed cells can be subjected to histological, immunohistological or molecular analysis. [41]

The cytology per impression of the conjunctiva will be done by the researcher using the device provided by the sponsor for this purpose, which may consist of a circular cell of approximately 10 mm in diameter, with a cellulose acetate filter millicell. After ocular surface anesthesia, with topical tetracaine, the researcher will ask the subject to expose the temporal surface of the eye to be evaluated and gently press the cell on the temporal conjunctiva (2 to 3 mm of the sclerocorneal limbus) for 5 seconds and remove the cell with a peeling technique (Illustration 1. Cytology per impression). Immediately fix with diethyl ether spray with one or two shots at 15 cm distance. The investigator will contact the Courier, within the first 24 hours, after the appointment designated by the sponsor for the shipment of the samples to histopathological analysis. You must complete the

requisition form provided by the investigator and attach it to the mailing. The format will consist of three sheets (1 original and 2 copies) which will be assigned as follows: original sheet for the Courier, 1 copy will be collected by the monitor and 1 copy will remain in the research center and will be filed in the corresponding folder to each research subject.

Illustration 1. Cytology per impression

The data of the histopathological report to be recorded in the CRF are: density of goblet cells and degree of squamous metaplasia according to the Nelson scale. (**See Table 5**)

In the visits required to perform this procedure, it will be done prior to the use of ocular surface stains.

Table 5. Nelson classification

Grade	Detail description of the epithelial cells	Characteristics of goblet cells
0	Small and round cells; Large nuclei, 1: 2 ratio with nuclear cytoplasm	Abundant goblet cells (> 500 cells / mm2), globose and oval with an intense PAS-positive staining of the cytoplasm.
1	Slightly enlarged cells; smaller nuclei, 1: 3 ratio with nuclear cytoplasm	Marked decrease in the number of goblet cells (350 to 500 cells / mm2) but still maintain their globose and oval shape and intense staining
2	Enlarged and polygonal cells; small nuclei, ratio 1: 4 to 1: 5 with nuclear cytoplasm	Marked decrease in the number of goblet cells (100 to 350 cells / mm2), less intense PAS - positive with poorly defined cell borders
3	Even larger and polygonal cells; small and pyknotic nuclei, 1: 6 ratio with nuclear cytoplasm	Few goblet cells (<100 cells / mm2)

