#### 6.4.3.4.1 Stains

Staining with green lysine and fluorescein

A drop of topical anesthetic will be instilled in the conjunctival cul-de-sac, then a second drop will be applied to the tip of the strip of green lysine and fluorescein and it will be allowed to slip towards the bottom of the sac. It is essential to quickly evaluate the staining, in sequence, first in the DO and then the OS, so that the observed patterns are equally bright. [19] See Annex 13.3 Oxford Scale

The value obtained according to the Oxford scale will be registered in the CRF.

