#### **Scrutiny Visit**

Some of these measurements should be complemented with those of the baseline visit and thus meet the eligibility criteria (see Schedule and study diagram), at the discretion of the PI.

- 1. Signature of informed consent.
- 2. General and ophthalmological clinical history.
- 3. Laboratory sample taking.
- 4. Pregnancy test.
- 5. Review of selection criteria
- 6. Visual ability
- 7. Density of goblet cells (Cytology per impression)
- 8. Intraocular pressure.
- 9. Eye comfort index
- 10. Evaluation of ocular signs and symptoms
- 11. Integrity of ocular surface
- a. Epithelial defects (TF and TVL)
- b. TRL
- 12. Subsequent segment evaluation.
- 13. Vital signs

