#### 6.6.1 Calculation of the sample size

Although there are no references on the calculation of the sample size in phase I studies, it was considered pertinent to perform it according to the presentation of adverse events referred by Christ T, in a randomized controlled trial of parallel groups, single blind, with randomization where

it was evaluated the efficacy and tolerance of a 5% dexpanthenol ophthalmic gel versus a 5% panthenol ointment in 48 subjects with corneal erosion, keratoconjunctivitis by UV radiation or similar conditions. The intervention consisted in the application of 1 cm of the gel and the ointment during 4 and 3 days, respectively. [20]

The percentage of good tolerance that was presented with the gel was 25%, so it is expected that no more than 10% of the subjects report a bad tolerance with the formulation proposed in this protocol.

The sample size was calculated using the formula for proportions

$$n = p (1 - p) \left( \frac{Z_{1-\alpha + Z_{1-\beta}}}{p - p0 - \delta} \right)^2$$

With a statistical confidence of 95% corresponding to the type I error, equal to 1.96, with a power of 80%, corresponding to the type II error, equal 0.84.

According to the previous calculation, the result is 19 subjects, which was increased by 20% for the probable losses. The total sample size required is 24 subjects. Therefore, each group will consist of 12 subjects, who will provide an eye for analysis.

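### Baseline staining may come from a visit without impression cytology while final staining always follows it, so baseline-to-final change in epithelial defects can include change made by the procedure

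*Combined protocol and SAP*

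**What the plan says.** - **What cytology does.** Section 6.4.3.2 describes a filter applied to the ocular surface "to remove the superficial layers of the epithelium". After topical anaesthesia the investigator is to "gently press the cell on the temporal conjunctiva (2 to 3 mm of the sclerocorneal limbus) for 5 seconds" and then peel the device off. It may be a circular cell of roughly 10 mm diameter.
- **Order.** The same section fixes the sequence: "In the visits required to perform this procedure, it will be done prior to the use of ocular surface stains".
- **What is graded afterwards.** Section 6.4.1.1 makes "Epithelial defects in cornea and conjunctiva" a primary safety variable. Under Stains (6.4.3.4.1), "The value obtained according to the Oxford scale will be registered in the CRF". One value is recorded. No section excludes the sampled area, grades it separately or sets a waiting time.
- **When.** The table in 6.5, with 6.5.1.1 to 6.5.1.4, puts staining at screening, basal, Visit 1 and final visits, and cytology at basal and final only.
- **Carry-over.** Footnote 1 of that table, which is attached to the basal staining entry, reads: "These measurements may be taken from the result of the screening visit, if it does not exceed the previous 7 days". Section 6.5.1.2 repeats the rule and leaves the choice to the principal investigator. Cytology is not on the carry-over list.
- **Conflict.** The Scrutiny Visit list in 6.4.4 includes "7. Density of goblet cells (Cytology per impression" as a screening procedure.
- **Use.** Section 5.5.2 sets an objective of describing safety through change in surface stains. Section 8.3.1 plans intra-group tests, but bases its safety conclusion on the comparison with the comparator. Section 6.6.1 states that "each group will consist of 12 subjects, who will provide an eye for analysis".

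**The concern.** A change from baseline can be read as a product effect only if both readings were taken under the same conditions. Here the final reading is always taken minutes after a procedure that removes epithelium from part of the tissue being graded. The baseline reading may have been taken on an undisturbed eye. Which of these applies is the investigator's choice for each subject, so the mismatch can differ between subjects and between centres.

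At stake are the baseline-to-final change in a primary safety variable and the intra-group test on it. Either could show an inert gel apparently worsening the ocular surface. The two descriptions of the screening visit add to this: whether a carried-over reading followed cytology depends on which section the site followed.

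**Working it through.** The plan gives no figure to reproduce, so the check starts by setting the visit descriptions side by side.

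**1. Condition of each staining reading**

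| Visit | Cytology in 6.5 table and 6.5.1 | Cytology in 6.4.4 | Condition of staining |
|---|---|---|---|
| Screening | No | Listed | Without cytology (table), or after it (6.4.4 with 6.4.3.2) |
| Basal, day 0 | Yes | Listed | After cytology if repeated; otherwise the screening value |
| Visit 1, day 3 ± 1 | No | No | No same-day cytology; 2 to 4 days after the basal one |
| Final, day 11 ± 1 | Yes | Listed | After cytology |

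**2. Which contrasts mix conditions.** With the table governing and baseline taken from screening, baseline to final compares a reading without cytology to one after it. If staining is repeated at the basal visit, baseline and final match, but Visit 1 then differs from both. So at least one within-subject contrast is unlike whichever source is chosen.

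**3. How few eyes matter.** There are 12 subjects per arm, one eye each. With k one-grade rises and no falls, the exact two-sided signed-rank p is 2 × 0.5^k:
- k = 5: 2 × 0.5^5 = 0.0625
- k = 6: 2 × 0.5^6 = 0.031

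An exact McNemar test on 6 versus 0 discordant pairs gives the same 0.031. Six procedure-made rises are therefore enough.

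**4. Illustration with assumed rates.** Suppose that the gel does nothing, that 20% of eyes are grade 1 at each reading, and that cytology adds one grade with probability q. With an unmatched baseline, per subject:
- P(rise) = 0.8 × [1 − 0.8(1 − q)] + 0.2 × 0.2q = 0.16 + 0.68q
- P(fall) = 0.2 × 0.8(1 − q) = 0.16(1 − q)
- Mean change = q grades

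The exact sign test at 0.05 on 12 subjects, as a stand-in for the planned Wilcoxon test, gives:

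| q | P(rise) | P(fall) | Rejects, unmatched | Rejects, both after cytology |
|---|---|---|---|---|
| 0.25 | 0.33 | 0.12 | about 7% | under 2% |
| 0.50 | 0.50 | 0.08 | about 34% | under 2% |
| 0.75 | 0.67 | 0.04 | about 76% | under 2% |
| 1.00 | 0.84 | 0.00 | over 99% | under 2% |

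With matched readings the mean procedure-made change is 0 for every q.

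**5. Between arms.** Both arms have the same procedure, so the expected addition is equal. If every eye gains one grade, the order of the grades is unchanged and so is the Mann-Whitney result, short of the top of the scale. Sensitivity is lost when some eyes gain and others do not. As an illustration, collapse the grade to present or absent and let cytology independently create a defect with probability q. Then P(defect) = 1 − (1 − p)(1 − q), and the arm difference shrinks by the factor (1 − q). At an assumed q = 0.7, 0% versus 40% becomes 70% versus 1 − 0.6 × 0.3 = 82%: a gap of 12 points instead of 40. The plan does not specify that collapse for the Oxford grade; Table 4 lists the grade as discrete.

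**The case against.** Several points count against making much of this, and most of them stand.

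- **The safety rule is between arms.** Section 8.3.1 draws no safety conclusion from the intra-group tests. A reader might infer that the mismatch biases the safety decision, or that equal added staining in both arms must hide a real difference. The documents support neither. The procedure is the same in both randomised arms, and a uniform shift leaves a rank comparison unchanged.
- **The effect has no stated size.** Section 6.4.3.2 supports removal of superficial cells. It does not say that 5 seconds of gentle pressure raises an Oxford grade, by how much or for how long. The rates above are assumptions.
- **Section 6.4.4 does not require two samplings.** A reader might infer that a site following it must sample the same area twice within days and so disturb the baseline goblet cell count. But its Scrutiny and Basal lists say that some measurements may complement each other at the investigator's discretion, so cytology could be done once. If it is done at screening, staining there also follows it, and the mismatch shrinks.
- **The order is not itself an error.** A reader might infer that the temporal zone must leave the primary grade. That would redefine a primary variable which names the conjunctiva. It is a debatable trade-off, not something the documents call for.

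One part survives. Under the schedule, an optional footnote lets a primary variable's baseline be read under a different condition from its final value. Section 5.5.2 makes change in stains an objective, so that change will be reported and interpreted.

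**Conclusion.** The point holds as a baseline mismatch affecting within-subject change. When the 6.5 table governs and the investigator carries over the screening grade, the baseline-to-final change in epithelial defects and its intra-group test can include change made by the procedure, to an extent that varies between subjects.

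The size is unknown. It rests on the inference that removing epithelium raises the Oxford grade, and on a rate that the documents do not give. Over assumed rates of 25% to 100%, within-arm false positives run from about 7% to over 99%, against under 2% when both readings follow cytology.

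The between-arm comparison is not biased in direction. On the graded scale it loses sensitivity only if the added staining varies between eyes. That deserves a note because safety is concluded from an absence of difference, with 12 per arm. The correction is worth making because it is cheap and removes the mismatch whatever the true rate.

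**What to change.** 1. Remove footnote 1 in 6.5, and the matching carry-over item in 6.5.1.2, for epithelial defects only. Baseline staining is then done at the basal visit after cytology, as at the final visit. The cytology-first order stays.
2. Keep the screening staining for eligibility and as the reference without same-day cytology for Visit 1. State that Visit 1 still follows the basal cytology by 2 to 4 days, so this match is closer but not perfect.
3. Reconcile the Scrutiny Visit list in 6.4.4 with the 6.5 table and 6.5.1.1 on whether cytology is done at screening.
4. Optionally, record the temporal conjunctiva separately and report a sensitivity analysis without it, leaving the primary grade unchanged. Zones not recorded at the time cannot be separated later, so decide this before enrolment.

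Cost: one staining repeated at a visit that already takes place, changes to protocol and CRF wording, and a little more analysis if the optional step is taken. No visit is added.
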